Appendix IV – Mayo Patient Survey

List of Abbreviations

3DCRT	3-D Conformal Radiation Therapy
AE	Adverse Event/Adverse Experience
CBCT	Cone Beam CT
CFR	Code of Federal Regulations
CRF	Case Report Form
CTV	Clinical Target Volume
DSMB	Data and Safety Monitoring Board
FDA	Food and Drug Administration
GCP	Good Clinical Practice
HIPAA	Health Insurance Portability and Accountability Act
IBTR	Ipsilateral breast tumor recurrence
IMRT	Intensity Modulated Radiation Therapy
IRB	Institutional Review Board
MRI	Magnetic Resonance Imaging
PHI	Protected Health Information
PI	Principal Investigator
PTV	Planning Target Volume
QOL	Quality of Life
RBE	Relative biologic effectiveness
RT	Radiation Therapy
SAE	Serious Adverse Event/Serious Adverse Experience
SOP	Standard Operating Procedure
XRT	X-ray Radiation Therapy

SCHEMA

N=25 patients

Study Design: This is a phase II trial to determine the effect of 25Gy in 5 fractions to the whole breast alone before breast conserving surgery.

1.0 Background

Breast Conserving Therapy and Breast Radiation

Breast cancer is the most common female malignancy in the United States with over 200,000 new cases being diagnosed annually. In the same manner, breast cancer mortality is one of the leading causes of cancer death among women. In breast cancer patients, the addition of whole breast radiotherapy after breast conserving surgery has been shown to result in improvement in rates of recurrence and survival for women with early stage and locally-advanced breast cancer.

Breast conserving therapy (BCT) refers to breast conserving surgery (BCS) and radiation therapy (RT) to eradicate any microscopic residual disease. The aim of BCT is to achieve equivalent overall survival compared with patients undergoing a mastectomy, with acceptable rates of local recurrence and good to excellent cosmetic results.

Six modern phase III trials have directly compared BCT to mastectomy and a meta-analysis of these trials has shown equivalent survival.¹⁻¹¹ Furthermore, the EBCTCG has shown the benefit of radiotherapy as an integral part of breast conserving therapy. Although the relative benefit of radiotherapy was similar for different patients, the absolute benefit will vary for different patient populations.¹²

Radiation therapy is considered an integral part of BCT. Despite this, certain subsets of patients may elect to forego radiotherapy given a small absolute benefit. CALGB 9343 and PRIME II have shown that selected elderly patients with early stage favorable breast cancer may safely omit radiotherapy after BCT.^{13,14}

Interestingly, a subtype population in the previously described Canadian study looking at the omission of radiotherapy demonstrated that the luminal A subtype of breast cancer (as defined by immunohistochemical analysis) was prognostic but not predictive of response to radiotherapy.¹⁵ Although the importance of radiation in the management of breast cancer is unquestioned, the ideal timing and overall effect of radiation on breast cancer based on different gene expression signatures is unknown at the present time.

Neo-adjvant Therapy for Breast Cancer

Neo-adjvant systemic therapy has been found to have similar outcomes to adjuvant chemotherapy after BCT¹⁶⁻¹⁸ However, certain advantages of neo-adjvant systemic treatment may include downstaging the tumor to allow for less extensive surgery, improved cosmetic outcomes, and reduced postoperative complications such as lymphedema.^{16,19} Neo-adjvant therapy also permits an early evaluation of the effectiveness of systemic therapy. The presence or absence of residual invasive cancer after neo-adjvant chemotherapy is a strong prognostic factor for the risk of recurrence.

In addition to the benefits as outlined above, neo-adjvant therapy gives us the opportunity to obtain imaging, tumor specimens, and blood samples prior to, during, at the time of surgery, and after the preoperative treatment. This information has enabled us to understand the true effect of neo-adjvant therapy on breast cancer. Furthermore, it has allowed us to understand tumor and patient-specific biomarkers with respect to response or resistance. Given the aforementioned findings, one would expect neo-adjvant radiotherapy to result in similar outcomes as postoperative radiotherapy, as seen previously with neo-adjvant systemic chemotherapy. The opportunity to treat patients with neo-adjvant radiotherapy would provide vital information to help the cancer community better understand the effect of radiation on tumor response, biomarkers, and DNA profiling of breast cancer. This information is crucial if we wish to better define the effect of radiotherapy on breast cancer and tailor our treatment doses to individual patients and their specific type of breast cancer.

Hypofractionated Breast Radiation

The most robust data for hypofractionated breast radiation comes from the United Kingdom. The Start A and Start B trials compared different hypofractionated radiotherapy regimens with the conventional regimen of 50Gy in 25 treatments over 5 weeks. The Start B trial, analyzed patients receiving a hypofractionated regimen of 40Gy in 15 treatments over 3 weeks, and found that the hypofractionated regimen resulted in less breast shrinkage, telangiectasia, and breast edema as compared to the standard arm.²⁰ No difference in arm edema or shoulder stiffness was seen among any of the hypofractionated arms as compared to 50Gy over 5 weeks. Interestingly, the hypofractionated 40Gy arm treated over 3 weeks had fewer distant events, which translated into an overall survival benefit at 10-year followup. The study concluded that hypofractionated radiotherapy of 40Gy in 15 treatments over 3 weeks was superior to the standard conventional 50Gy in 25 treatments over 5 weeks in terms of adverse events and cancer specific outcomes.

The UK Fast Trial published the cosmetic results of 390 patients undergoing conventional and hypofractionated radiotherapy.²¹ A hypofractionated regimen of 30Gy and 28.5Gy in 5 treatments over 5 weeks was compared to a longer conventional regimen of 50Gy in 25 treatments over 5 weeks. At 2 years post-randomization, 20.8% of patients had mild change and 6.2% had marked change in photographic breast appearance. There was no difference observed for any of the dosimetric parameters confirming the safety of a more hypofractionated approach. Furthermore, the initial results showed three-year rates of physician-assessed moderate/marked adverse effects in the breast were similar for 28.5Gy in 5 treatments over 5 weeks when compared with 50Gy in 25 treatments over 5 weeks.²²

The Fast Forward Trial has also published comparable acute toxicity among 40Gy in 15 treatments over 3 weeks, and 27Gy or 26Gy in 5 treatments over one week.²³ 190 and 162 patients were recruited for two studies. In the first sub-study, evaluable patients with grade 3 RTOG toxicity were: 13.6% with 40Gy in 15 fractions; 9.8% with 27 Gy in 5 fractions; and 5.8% with 26 Gy in 5 fractions. In the second sub-study only one patient presented with G3 CTCAE toxicity in the 27 Gy in the 5 fraction arm.

Preoperative Radiation

Preoperative radiotherapy has been used successfully in the past for the management of breast cancer.²⁴⁻²⁸ Preoperative radiotherapy in patients with locally advanced breast cancer has shown excellent loco-regional control rates even when few patients receive systemic therapy. Pathologic complete response (pCR) was also associated with improved outcomes in patients undergoing preoperative radiotherapy.²⁸ Matuschek et al. reported that pCR after neo-adjuvant chemo-radiation was 56% for node-positive cases (cN+). The multivariate analysis of this study revealed that a longer time interval to surgery increased the probability for a pCR (HR 1.17 [95% CI 1.05–1.31], p<0.01). Importantly, pCR was the strongest prognostic factor for long-term survival in patients (HR 0.28 [95% CI 0.19–0.56], p<0.001).²⁷

Other studies have looked at hypofractionated preoperative radiation as well. Researchers at the University of Maryland evaluated the impact of preoperative hypofractionated radiation on pathologic complete response (NCT01014715). Bondiau et al²⁹ analyzed five different dose levels during preoperative chemotherapy in high-risk breast cancer patients. Dose levels of 19.5Gy, 22.5Gy, 25.5Gy, 28.5Gy and 31.5Gy were used, with only one grade 3 treatment related AE seen at 8 months. Moreover, pCR was seen in 36% of the patients. However, no pCR was observed in the first dose level of 19.5 Gy, and the majority of pCR (67%) were observed in level 3 (25.5Gy). Given the response with doses of 25.5Gy and higher, a dose of 25.5Gy was selected for future hypofractionated preoperative trials. Horton et al also evaluated extreme preoperative hypofractionated radiation using a single treatment of intensity

modulated radiation therapy with 15 Gy, 18 Gy, or 21 Gy to the tumor with a 1.5-cm margin.³⁰ No dose limiting toxicity was seen. Tumor response was difficult to evaluate given that surgery was done 10 days after radiotherapy. Multiple studies have shown the safety and excellent cosmetic results of preoperative radiation either in a hypofractionated approach or with standard fractionation. Furthermore, the use of preoperative radiotherapy alone or concurrently with chemotherapy has also been tested and reveals excellent results with minimal toxicity. The literature provide a very compelling argument favoring the use of hypofractionated radiation therapy to a dose of 25Gy in 5 fractions, followed by surgery 8 weeks thereafter to maximize radiation response, as proposed in our current study.

To assess the response of hypofractionated radiation therapy before radiation we would use residual cancer burden in the surgical specimen. We defined a pathological complete response (pCR) as a residual tumor burden of 0-1.³¹

Boost

The EORTC trial showed a small improvement in local control with the use of a boost (4% at 10 years). However, severe breast fibrosis was increased by a similar magnitude at 10-years (3%). Furthermore, no difference was seen between the two groups in terms of breast cancer mortality, overall incidence of breast cancer-related events, disease-free survival, or overall survival.³² Since, the use of boost has shown an increase in severe breast fibrosis without an improvement in breast related outcomes, we have elected not to use a boost for this trial.

Predicting response to RT

There has been much interest recently in developing more useful biomarkers to identify patients risk and response to radiation therapy in breast cancer. Clinico-pathologic factors as used in the CALGB 9343 study or PRIME II, including age, tumor size, and hormone receptor status, remain imperfect in their risk stratification, and thus identifying overall risk and radiation response remains an unmet clinical need.^{13,14} The Danish study has shown that post-mastectomy radiation improved survival in certain cohorts of patients over others.^{33,34} However, different studies suggest different benefits based on these biomarkers. These findings lend to the necessity of additional research regarding the response of radiation in cohorts of patients treated uniformly and for whom gene expression profiling is done. Similar to chemotherapy tests such as OncotypeDx and Mammaprint, biomarker testing can ultimately prove beneficial to further delineate the benefit of radiotherapy in our breast cancer patients.

Ideally, breast cancer response to radiation should be addressed by studying the direct effect of radiation on the tumor cells. Gene profiling before and after radiotherapy would help better define the effect of radiation over breast cancer and associated predictive DNA signatures, which remains an active area of interest in the breast cancer field.

Through our research, we hope to better define the breast cancer response to hypofractionated radiation without the confounding factors of other systemic treatments. This research would provide a unique opportunity to address the effect of radiation and describe DNA signatures more likely to be associated with response. We aim to further understand the effect of radiation on cancer cells and, thus individualize the dose and timing of radiation therapy that is necessary to eradicate breast cancer cells.

Summary

At the present time, very little data exists regarding the distinct changes that occur with radiotherapy in the cancer itself. Breast cancer represents a heterogeneous disease with distinct clinical features that can be predicted by differences in the DNA. The analysis of tumor mutation signatures may lead to a better understanding of the effect of radiotherapy in breast cancer. Preoperative radiation of the intact tumor with a hypofractionated regimen can potentially decrease toxicity by allowing the delivery of treatment to intact breast tissue. The potential advantages of preoperative radiation therapy include the delivery of radiation in the intact breast when radiation can be more efficacious as more oxygen can be available in the tissue. Furthermore, complications and cosmetic results are expected to be lower in pre-operative radiotherapy before surgery, as there have been no changes in blood supply to the breast. This lends to the possibility of using lower doses of radiotherapy to patients, and potentially better cancer associated clinical outcomes for our breast cancer patients.

2.0 Goals

2.1 Primary Objectives

2.1.1 To determine the pathologic complete response (pCR) rate after hypofractionated radiotherapy to the whole breast alone, based on the postsurgical specimen. We define a pCR as residual cancer tumor burden of 0-1.

2.2 Secondary Objectives

- 2.21 To evaluate acute and late toxicity with preoperative radiation including grade ≥ 2 pneumonitis.
- 2.22 To estimate the 5-year locoregional control, distant recurrence, invasive disease-free survival, cause-specific survival, and overall survival.

2.3 Correlative and Exploratory

- 2.31 To evaluate patient-reported outcomes.
- 2.32 To evaluate clinical features, treatment technique, dose-volume parameters, histologic and genetic variants associated with adverse events, and fair and poor cosmetic outcomes or unplanned surgical intervention.
- 2.33 Evaluate tumor mutation signatures before and after radiation; correlate tumor mutation signatures before and after radiation with pathologic information at the time of surgery.
- 2.34 To describe the pathologic changes seen in breast cancer patients with preoperative radiation.

3.0 Patient Eligibility

3.1 Inclusion Criteria

- 3.1.2 Age ≥ 18 years.
- 3.1.3 Histological confirmation of breast cancer.
- 3.1.4 Clinical Stage T0-T2 N0 M0.
- 3.1.5 ECOG Performance Status (PS) 0 to 2. (Appendix I)
- 3.1.6 Able to and provides IRB approved study specific written informed consent.
- 3.1.7a Study entry must be within 120 days of last biopsy (breast).
- 3.1.7b Able to complete all mandatory tests listed in section 4.0.
- 3.1.7c Willing to return to enrolling institution for follow-up (during the active monitoring phase of the study).
- 3.1.8 Planned breast surgery and indications for whole breast radiotherapy.
- 3.1.9 No neo-adjuvant therapy

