6.0 Registration

6.1 Registration Procedures

- 6.1.1 Patient will be registered to the study when they have consented, met eligibility criteria, and have been logged into the Research Participant Tracking (Ptrax) system.
- 6.1.2 Baseline tests/procedures (see section 4.0) will be completed within the guidelines specified on the test schedule.
- 6.1.3 All patients meeting eligibility criteria who have signed a consent form and who have completed treatment will be evaluable for the primary analysis. All patients completing treatment as per the study pre-op RT followed by breast conserving surgery will be used to determine the protocol accrual.
- 6.1.4 Patients consented and enrolled will be monitored in the registry, if patients signed our registry consent (IRB 16000492). All patient meeting accrual as defined in 6.1.3 will be analyzed per study.

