Unplanned surgical intervention will be adjudicated by a plastic surgeon and a general surgeon.

11.5 Pathologic complete response. At time of surgery the residual tumor would be measured and a score of 0-1 would be considered a pCR. Residual cancer burden (RCB) measurement is currently considered SOC for all three sites for surgical specimens after neo-adjuvant therapy. We would use the current grading used at the three Mayo sites to determine RCB.³¹

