16.2 Primary and Secondary Endpoints

16.21 Primary Endpoint: The pathologic complete response (pCR) rate observed at time of definitive surgery in breast cancer patients receiving preoperative ionizing radiation. A residual tumor cancer burden 0-1 would be considered a pCR.³¹ All patients meeting eligibility criteria who have signed a consent form and who have begun treatment will be evaluable for the endpoint.

16.22 Secondary Endpoints:

16.221 Acute and late adverse events including grade ≥ 2 pneumonitis.

16.223 Locoregional control, invasive disease-free, distant recurrence, disease-free survival, cause-specific survival, overall survival.

The following definitions are used for the secondary endpoints of interest:

- *Pathologic complete response*: We defined a pathological complete response (pCR) as a residual tumor burden of 0-1 in the surgical specimen.³¹
- *Acute adverse events* (up to 180 days post-RT): any adverse event, regardless of attribution, that occurs in the first month post-RT.
- *Late adverse events* (up to 5 years post XRT): any adverse event that occurred after the first month post-RT and up to 5 years post-RT.
- *Ipsilateral breast tumor recurrence (IBTR)*: this is defined as local recurrence from trial registration as a first event at 5 years. IBTR is defined as both invasive and non-invasive breast cancer involving the same breast parenchyma as the original tumor.
- *Regional recurrence*: invasive breast cancer in the axilla, regional lymph nodes, chest wall, and skin of the ipsilateral breast at 5 years.
- *Distant recurrence*: metastatic cancer that has either been biopsy confirmed or clinically diagnosed as recurrent invasive breast cancer at 5 years.
- *Invasive disease-free survival*: this is defined as the time from study registration until the occurrence of one of the events in a composite endpoint. This endpoint includes invasive IBTR, regional invasive breast cancer recurrence, distant breast cancer recurrence, death due to any cause,
- *Disease-free survival*: this is defined as the time from study registration until the occurrence of one of the events in a composite endpoint. This endpoint includes any IBTR, regional invasive breast cancer recurrence, distant breast cancer recurrence, death due to any cause,

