Pathologic complete response (pCR) will be assessed at the time of definitive surgery. The largest success proportion where the proposed treatment regimen would be considered ineffective in this population is 5%, and the smallest success proportion that would warrant subsequent studies with the proposed regimen would be 20%. The following Simon's Optimum design uses 22 evaluable patients to test the null hypothesis that the proportion of successes is at most 5%

16.41 Decision Rules:

16.411 If 2 or fewer successes are observed in the first 22 evaluable patients that have a definitive surgical procedure, we will consider this regimen to be ineffective in this patient population. If 3 or more successes are observed in the first 22 evaluable patients, we may recommend further testing of this regimen in subsequent studies in this patient population.

16.412 Over Accrual: If more than the target number of patients are accrued, the additional patients will not be used to evaluate the stopping rule or used in any decision making process.

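### Clinical T0 is eligible and pCR is scored without a baseline, yet no evaluability rule asks for tumour before RT, so a 3-of-22 pass may partly reflect case mix

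*Combined protocol and SAP*

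**What the plan says.** **Entry.** Section 3.1.4 admits "Clinical Stage T0-T2 N0 M0" and 3.1.3 asks for "Histological confirmation of breast cancer". T0 is not defined. None of the listed criteria sets a minimum size or asks that tumour remain after the biopsy. Study entry may be up to 120 days after the last biopsy (3.1.7a), and RT may start up to 180 days after it (7.0).

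**Endpoint.** Section 11.5: "At time of surgery the residual tumor would be measured and a score of 0-1 would be considered a pCR". Sections 2.1.1 and 16.21 use the same threshold. None of them compares the specimen with the tumour at baseline.

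**Who counts.** Section 6.1.3: "All patients meeting eligibility criteria who have signed a consent form and who have completed treatment will be evaluable for the primary analysis". Section 16.21: "All patients meeting eligibility criteria who have signed a consent form and who have begun treatment will be evaluable for the endpoint", and 16.51 agrees with it. Section 16.411 adds that a definitive surgical procedure has taken place. These statements differ on whether treatment must be begun or completed, which is a separate matter. None mentions tumour before RT.

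**Decision rule.** Section 16.4: "The largest success proportion where the proposed treatment regimen would be considered ineffective in this population is 5" per cent. The alternative is 20%. Section 16.411: "If 3 or more successes are observed in the first 22 evaluable patients, we may recommend further testing". Section 16.44 gives a significance level of 0.10.

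**Elsewhere.** There is no stratification (5.1). The tumour-size categories in 12.0 begin at 0 cm and are only descriptive. Section 16.5 plans no analysis of pCR by baseline tumour.

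**The concern.** An absolute threshold at surgery measures response only if there was something to respond. Taking T0 to mean no evident primary, an eligible patient whose lesion was wholly removed at biopsy could reach RCB 0-1 whatever the radiation did, and would still be one of the 22.

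The design is sensitive to single patients. The null expects 22 × 0.05 = 1.1 successes and the bar is 3. A result of 3/22 (13.6%) passes. If one of those three had no tumour before RT, the remaining patients show 2/21 (9.5%), and two successes would not have passed. At stake is whether a recommendation for further testing can be credited to the regimen.

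**Working it through.** **Inputs from the plan.** n = 22, pass at 3 or more, null 5%, alternative 20% (16.4, 16.411); level 0.10 (16.44); allowance of 3 extra patients (16.42).

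**Assumptions.** The documents do not give the frequency f of patients with no tumour before RT, or the number k of them among the 22. Nor do they give such a patient's probability s of scoring RCB 0-1. I take s = 0.25, 0.5 and 1; values below 1 allow for undetected disease.

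**Step 1: the plan's own table.** P(Bin(22, p) ≥ 3):

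| p | 0.05 | 0.10 | 0.15 | 0.20 | 0.25 |
|---|---|---|---|---|---|
| Plan (16.44) | 0.09 | 0.38 | 0.66 | 0.85 | 0.94 |
| Recomputed | 0.0948 | 0.3800 | 0.6618 | 0.8455 | 0.9394 |

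The table reproduces, so the design arithmetic is not in question.

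**Step 2: 5% applies to the whole eligible population.** By definition the null pass probability is at most 0.0948 when patients are drawn from a population with an overall rate of 5%. Fixing exactly one patient without tumour (k = 1) and holding the average rate at 5%, the rate in the other 21 is q = (1.1 − s)/21. The pass probability is s·P(Bin(21, q) ≥ 2) + (1 − s)·P(Bin(21, q) ≥ 3).

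| s | q | P(pass) |
|---|---|---|
| 0.25 | 4.0% | 0.090 |
| 0.5 | 2.9% | 0.070 |
| 1 | 0.5% | 0.004 |

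The level stays within 0.10. What changes is the meaning: an overall rate of 5% then corresponds to a lower rate among patients who had tumour to treat.

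**Step 3: 5% applies to patients with tumour, frequency f.** The overall rate is p = f·s + (1 − f)·0.05 and the pass probability is P(Bin(22, p) ≥ 3).

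| f | s = 0.25 | s = 0.5 | s = 1 |
|---|---|---|---|
| 0 | 0.095 | 0.095 | 0.095 |
| 0.5% | 0.099 | 0.105 | 0.116 |
| 1% | 0.104 | 0.115 | 0.140 |
| 2% | 0.113 | 0.137 | 0.191 |

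Example: f = 1%, s = 1 gives p = 0.01 + 0.99 × 0.05 = 0.0595 and P = 0.140.

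**Step 4: the same reading, given exactly one such patient.** P = s·P(Bin(21, 0.05) ≥ 2) + (1 − s)·P(Bin(21, 0.05) ≥ 3) = s × 0.2830 + (1 − s) × 0.0849. This gives 0.134, 0.184 and 0.283. The share of passes that would fail without that patient's success is s·P(Bin(21, 0.05) = 2)/P = s × 0.1981/P, or 37%, 54% and 70%. One in 22 is 4.5%, so these figures show what one such patient would do; they do not estimate how often it would happen.

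**Step 5: operating characteristics of a restricted decision set.** Bar kept at 3:

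| n | P(pass) at 5% | P(pass) at 20% |
|---|---|---|
| 22 (replaced) | 0.095 | 0.846 |
| 21 | 0.085 | 0.821 |
| 20 | 0.075 | 0.794 |
| 19 | 0.067 | 0.763 |

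**The case against.** **Such patients should be rare.** Entry needs biopsy-proven cancer, planned breast surgery and an indication for whole-breast RT (3.1). Diagnostic tumour tissue is mandatory and described as a core biopsy (17.1). Simulation CT uses contrast to define the tumour (7.48), and a tumour volume is contoured with coverage goals (7.613, 7.8.2). T0 may be loose staging wording. This largely stands, and it limits the size of the problem. It does not close the gap. Biopsy material shows cancer at biopsy, not tumour left afterwards. The contour may be drawn around a marker, and neither step is tied to evaluability.

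**Text is missing.** The body of the section 4.0 schedule is not in the text available, and 3.1.7b makes its mandatory tests a condition of entry. It may list baseline imaging. That stands as a limit, although no visible evaluability rule refers to an imaging finding.

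**A reader might infer that the trial's type I error is really 0.28.** The documents do not support that. Section 16.4 sets 5% for the population under study, most naturally the eligible one, and there the level holds. The figure 0.283 needs three assumptions at once: 5% moved to a subgroup the plan does not name, exactly one such patient, and certain success.

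**A reader might infer a conflict with the stated aim of an unconfounded response.** The Background says "we hope to better define the breast cancer response to hypofractionated radiation without the confounding factors of other systemic treatments". That concerns systemic therapy, not baseline tumour, so there is no such conflict.

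**A reader might infer that in-situ disease is a second route to unearned successes.** The documents do not say how in-situ-only disease scores, so that is not established.

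**Conclusion.** The gap is real and minor. An undefined T0 stage is eligible, success is absolute, and no visible rule on who counts asks for tumour before RT. With a bar of 3 against 1.1 expected, one patient with nothing left to treat could turn a fail into a pass.

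Under the natural reading of the 5% null there is no breach of the 0.10 level; a positive result may simply owe something to case mix. If 5% was meant for patients with tumour, the null pass probability moves from 0.095 to between 0.099 and 0.191 over assumed frequencies of 0.5% to 2%, and to 0.134-0.283 if exactly one of the 22 is such a patient. The frequencies and success probabilities are assumptions, T0 is read as no evident primary, and the true number may be zero. The power table in 16.44 is correct as it stands.

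**What to change.** 1. **3.1.4:** define T0, or correct the stage range if T0 is not intended.
2. **16.21, 16.411, 16.51:** state that the 22 decision patients have a primary tumour documented before RT. Judge this from existing biopsy pathology and baseline or planning imaging, and record it before RT starts, so before pCR is known. Count a marked lesion as documented unless the biopsy record and imaging show no residual lesion.
3. **16.4:** state that 5% and 20% refer to these patients.
4. **Other patients:** report their pCR separately and keep them in the safety and secondary analyses.
5. **Histology:** report pCR by histology descriptively. Do not add an invasive-histology requirement, which would narrow the tested population on a premise the documents do not establish.

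**Cost.** Wording and one status field, relying on pathology and imaging already obtained; the section 4.0 table should be checked to confirm the imaging. Replacements draw on the 3-patient allowance in 16.42, which also covers ineligibility, cancellation and major violations. With replacement to 22, alpha and power stay at 0.095 and 0.846. With one patient not replaced (n = 21, bar kept at 3) they are 0.085 and 0.821. The plan should say which applies.
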